6.3 PARTICIPANTS & DATA COLLECTION

We will recruit men and women aged ≥ 18 years with Ulcerative Colitis who are able to provide written informed consent will be recruited from gastroenterologists as well as via community/social media advertising in the greater Sydney area.

Participants with UC Inclusion Criteria:

1. Aged ≥ 18 in 2018
2. Ulcerative colitis (UC) >3 months' duration of any extent.
3. Stable medication. No changes to medication or therapies in the preceding 4 weeks.

Participants with UC Exclusion Criteria:

1. Prior or concomitant fecal microbiota transplantation or any rectal preparations currently.
2. Antibiotic/anti-tuberculosis treatment for any reason during the study period or in the preceding 4 weeks.
3. Probiotic supplements or biological/monoclonal antibody agents during the study period or in the preceding 12 weeks. Food based probiotics such as yoghurt and kefir will be allowed.
4. Significant prior gastrointestinal surgery (e.g., colon resection, colectomy, appendectomy) or clinical evidence of any comorbid chronic disease that may interfere with the patient's ability to enter the trial and undertake the intervention planned.
5. Coexistent serious autoimmune disease such as rheumatoid arthritis or systemic sclerosis.
6. Planned major surgery within the first 3 months after randomization.
7. Pregnancy or female planning pregnancy within the first 3 months after randomization.
8. Participation in another clinical trial for with concurrent participation is deemed inappropriate.
9. Daily consumption of olive based product(s) in any form (including oil, pickles, tapenade, spreads, and supplements) as determined by the diet history and medication list

10. Currently on a special diet in which participation is deemed inappropriate (e.g. low residue diet, liquid diet, low fat diet)

We will also recruit men and women aged ≥ 18 years with no significant chronic or acute disease who are able to provide written informed consent to participate in the study as the healthy control group. Recruitment will be achieved through community/social media advertising in the greater Sydney area alongside the recruitment strategy for participants with UC.

Healthy Control Inclusion Criteria:

1. Aged ≥ 18 years in 2018
2. Willing to be randomized into one of the two study arms and participate in the intervention prescribed
3. Stable medication. No plans to modify current medication or supplement regiment during the study period and no changes to medication in the preceding 4 weeks.

Healthy Control Exclusion Criteria:

1. Those in remission from UC as defined by an assessment by a gastroenterologist.
2. History of fecal microbiota transplantation or any rectal preparations including enemas.
3. Antibiotic/anti-tuberculosis treatment for any reason during the study period or in the preceding 4 weeks.
4. Probiotic supplements or biological/monoclonal antibody agents during the study period or in the preceding 12 weeks. Food based probiotics such as yoghurt and kefir will be allowed.
5. Chronic or acute disease requiring medical or therapeutic intervention including but not limited to diabetes, IBD, chronic kidney disease, cancer, IBS.
6. Coexistent serious autoimmune disease such as rheumatoid arthritis or systemic sclerosis.
7. Significant prior gastrointestinal surgery (e.g., colon resection, colectomy, appendectomy) or clinical evidence of any comorbid chronic disease that may interfere with the patient's ability to enter the trial and undertake the intervention planned.
8. Planned major surgery within the first 3 months after randomization.
9. Pregnancy or female planning pregnancy within the first 3 months after randomization.
10. Participation in another clinical trial for with concurrent participation is deemed inappropriate.
11. Daily consumption of olive-based product(s) in any form (including oil, pickles, tapenade, spreads, and supplements) as determined by the diet history and medication list
12. Currently on a special diet in which participation is deemed inappropriate (e.g. low residue diet, liquid diet, low fat diet) or under the supervision of an Accredited Practising Dietitian or other relevant healthcare professional

6.4 SAMPLE SIZE

Power Calculations:

At the time of writing, there were limited published papers identifying the effects of diet on active Ulcerative Colitis. We identified three studies on dietary intervention; 1 randomized controlled trial of a single food component (22) and two uncontrolled trials of a comprehensive diet intervention (23, 24). Only the two uncontrolled studies had enough information to allow for the calculation of an effect size. Hedges' bias corrected effect sizes were calculated from published means and standard deviations of a single group, pre-post study involving a dietary intervention over 8 weeks (23) and 6 weeks (24) (Table 1).

The effect size of a dietary intervention in active Ulcerative Colitis calculated from these studies were 0.917 (23) and 2.638 (24) respectively. With consideration to the current study design which includes adult populations and the use of the same scoring tool, we have selected the paper by Konijeti, et. al (24) to estimate sample size.

Table 1

Citation	Outcome	Baseline	Post dietary intervention	Mean difference	Pooled SD	Effect size	Sample size (n total)
Suskind et al., (23)	Pediatric Ulcerative Colitis Activity Index	28.3 (8.8)	6.7 (2.9)	- 21.6	6.6	0.917634	48
Konijeti et al., (24)	Partial Mayo Score	5.8 (1.2)	1.2 (2.0)	- 4.6	1.6	2.638281	16

The Partial Mayo Score is a validated 9-point, non-invasive method of assessing disease severity in Ulcerative Colitis comprising of stool frequency, bleeding, and subjective assessments of disease activity. Remission is set at ≤ 1 , Mild Disease between 2-4, Moderate Disease between 5-6, and Severe Disease ≥ 7 (25).

Based on the available evidence, we hypothesize that EVOO consumption would elicit a similar reduction to average Mayo Score in the intervention group compared to those randomized into the usual care group. Due to the single dietary intervention used in this study and accounting for the uncontrolled study cited, a conservative approach to estimate effect size was implemented.

We calculated effect size based on a 2 point (22%) reduction in the Partial Mayo Score (less than half of the mean difference cited in literature), with alpha 0.05 and beta 0.8. Effect size was calculated to be 1.25, with a sample size of 12 participants per group (24 individuals with Ulcerative Colitis randomized to either the intervention or usual care) required to determine changes in disease activity post intervention. Accounting for a 16% dropout rate which occurred in both studies selected, we will aim to recruit 28 participants with Ulcerative Colitis.

With consideration to those without a history of Inflammatory Bowel Disease, we will also aim to recruit an equal number of participants. Due to the limited evidence available on the effects of EVOO consumption on the gut microbiome and inflammatory markers in apparently healthy individuals, the recruitment number of apparently healthy controls are not based on any hypotheses on the differences between those living with UC and non-IBD cohorts subjected to EVOO consumption or dietary intervention. In total, we will aim to recruit 56 participants for this study; 28 individuals with UC and 28 individuals without a history of IBD.

Expected duration of the study and start times

It is expected that the study will take four years to complete. This includes 6 months to set up the study, including recruitment and training of the study personnel, procuring study resources, and preparation of the recruitment and study materials.

It is expected that recruitment will begin no later than April 2019. We are aiming for a conservative estimate of 1 participant per week, and means all participants will be recruited by June 2020, however additional time has been allocated to account for delays related to other investigations, work and travel arrangements, and recent changes to therapy.

The baseline assessments will start in April 2019 and end latest by August 2020.

The post-intervention assessments will start in May 2019 and end by November 2020, with additional time allocated to account for unexpected delays in recruitment and assessment.

The main outcome publication will be prepared by early to mid-2021. Table 2 illustrates the overall project schedule.

Table 2. Colonic Project Schedule

	2018	2019				2020				2021
	Oct-Dec	Jan-Mar	Apr-Jun	Jul-Sep	Oct-Dec	Jan-Mar	Apr-Jun	Jul-Sep	Oct-Dec	Jan-Mar
Study protocol and ethics approval	X	X								
Set-up of the study	X	X								
Recruitment of participants			X	X	X	X	X			
Baseline assessments			X	X	X	X	X	X		
Post-intervention assessments				X	X	X	X	X	X	
Preparation of main outcome publication								X	X	X

The research team will assess all outcomes at baseline, mid and post-intervention. Data collection and entry will be performed using both paper based forms and online via RedCap data managing system.

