We hypothesise that replacement of usual dietary fats with extra virgin olive oil will improve disease activity scores in those with Ulcerative Colitis relative to the usual care control group. Additionally, the impact of extra virgin olive oil consumption will be distinct between those with active UC and healthy controls. Using results from past diet studies in UC, the effect size of diet was estimated to be 0.917. Sample size was calculated at an alpha of 0.05 and beta 0.8, resulting in an estimated sample size of 60 participants.

The COLONIC will be a novel study identifying the impact of dietary fat types on the disease expression of UC and changes to the gut microbiota in comparisons to healthy subjects without IBD.

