6.2 STUDY DESIGN

Participants will be divided into two groups; individuals with Ulcerative Colitis (n: 30) and healthy controls (n: 30). Participants within these two groups will be randomised after screening in a 1:1 ratio to nutrition intervention or usual care. We will use a concealed, computer-generated sequence of randomly permuted variable blocks of four or 6, stratified for presence/absence of disease and sex, generated by an online program created by a statistician not otherwise involved in the study, available at www.randomization.com. Randomisation will occur at the completion of the baseline assessment and will be concealed by a statistician not otherwise involved in the study. The baseline assessor will confirm the participant's assignment at the end of the study with this staff member and communicate the study allocation to the participant to discuss next steps.

Intervention arms

Treatment Group: Replacing free fats with extra virgin olive oil

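### The sample size is stated at a beta of 0.8, but the printed 12 per group is the answer for a power of 0.80 (beta 0.20): a mislabelled error rate that leaves the sample size unchanged

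*Protocol*

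**What the plan says.** Section 6.4 (Sample Size) starts from a difference on the Partial Mayo Score: "We calculated effect size based on a 2 point (22%) reduction in the Partial Mayo Score". Table 1 in the same section gives a pooled SD of 1.6 for that score. The error rates and the result are given together: "with alpha 0.05 and beta 0.8. Effect size was calculated to be 1.25, with a sample size of 12 participants per group", that is, 24 participants with UC. The text then allows for dropout: "Accounting for a 16% dropout rate which occurred in both studies selected, we will aim to recruit 28 participants with Ulcerative Colitis". With an equal number of healthy controls the total is 56. Section 6.2 has participants "randomised after screening in a 1:1 ratio to nutrition intervention or usual care".

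The Synopsis uses the same label with other figures. There, "the effect size of diet was estimated to be 0.917", and "Sample size was calculated at an alpha of 0.05 and beta 0.8, resulting in an estimated sample size of 60 participants".

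Section 6.4 places its calculation under a subheading on power, but neither it nor the Synopsis gives a figure for power, and neither defines beta in any special sense.

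**The concern.** In a sample-size statement, beta next to alpha is the type II error rate, and power is one minus beta. A beta of 0.8 therefore means that the trial would miss its target effect four times in five. No one would plan a trial on that basis, and the number of participants printed in the same sentence does not fit it.

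What is at stake is the accuracy of a stated design property, not the design. Disease activity by Partial Mayo Score is a primary outcome (section 9.1), and the type II error is what a reader consults when judging a null result on it. The mislabel appears twice, once in the Synopsis, which is the part most easily copied into a registration or a paper. A reader can recover the intended meaning only by redoing the calculation.

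**Working it through.** **Inputs.** Difference 2 points (section 6.4); SD 1.6 (Table 1); d = 2 / 1.6 = 1.25, which matches the printed effect size. Allocation 1:1 (section 6.2). Alpha 0.05; its sidedness is not stated, so I take two-sided and also try one-sided.

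**Normal approximation.** n per group = 2 × (z for alpha + z for power)² / d², with d² = 1.5625.

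- 0.8 read as power: 2 × (1.960 + 0.842)² / 1.5625 = 2 × 7.849 / 1.5625 = 10.05, rounded up to 11.
- 0.8 read as beta (power 0.20): 2 × (1.960 − 0.842)² / 1.5625 = 2 × 1.251 / 1.5625 = 1.60, rounded up to 2.

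**Two-sample t-test (noncentral t).** Degrees of freedom 2n − 2, noncentrality d × √(n/2).

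| Reading of 0.8 | n per group, two-sided 0.05 | Rounded up |
|---|---|---|
| Power 0.80 (beta 0.20) | 11.09 | 12 |
| Beta 0.80 (power 0.20) | 2.80 | 3 |

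The printed 12 is reproduced by the first row. The second row is a quarter of it.

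**Power at particular sizes** (t-test, two-sided 0.05, d = 1.25):

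| n per group | Power | Beta |
|---|---|---|
| 3 | 22.0% | 0.78 |
| 11 | 79.6% | 0.20 |
| 12 | 83.3% | 0.17 |

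At n = 12 the noncentrality is 1.25 × √6 = 3.06 on 22 degrees of freedom. The normal approximation gives 86.5% at n = 12.

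**One-sided check.** At one-sided 0.05, power 0.80 needs 8 (normal) or 9 (t-test, 8.68) per group, and a literal beta of 0.8 needs 1 or 2. Neither gives 12. A one-sided test at power 0.90 also rounds up to 12 (11.71), but 0.90 is printed nowhere. The reading that fits both the printed 0.8 and the printed 12 is power 0.80, two-sided.

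**The Synopsis.** With d = 0.917, d² = 0.841.

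- Power 0.80: normal 2 × 7.849 / 0.841 = 18.7, so 19 per group; t-test 19.68, so 20 per group, or 40 for one two-arm comparison.
- Literal beta 0.8: 3 (normal) or 5 (t-test, 4.09) per group.
- If the 60 were one comparison of 30 per group, power would be about 94%.

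So 60 does not follow from 0.917 under either meaning of 0.8.

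**The case against.** The strongest reply is that this is notation and nothing more. The subheading speaks of power, 0.8 is the customary value for power, and the inputs give exactly 12 per group once 0.8 is read that way. That stands. No number in section 6.4 has to change, and the point should carry little weight.

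Three stronger readings are tempting, and the documents do not support them.

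- A reader might infer that the trial has 20% power for its target effect. It does not: 20% power would go with 3 per group, and the protocol plans 12 evaluable per group.
- A reader might treat the gap between the printed beta of 0.80 and the beta of about 0.17 at n = 12 as the size of the error. That gap of 63 points measures the mislabel; its effect on the design is nil.
- A reader might count the unstated sidedness of alpha as a further fault. With 0.8 as power, the printed 12 already points to a two-sided test, and a protocol may leave that statement to the statistical analysis plan. It is convenient to add it while correcting the line, but it is not a finding.

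It is also fair to object that 83% power should not be read as a property of the planned analysis. Section 6.5 plans a covariate-adjusted repeated-measures mixed model for the group-by-time interaction, and the SD of 1.6 comes from one uncontrolled pre-post group. The 83% holds only for a plain two-sample t-test with that SD, and the protocol should say so if it prints the figure.

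What survives is that a design error rate is stated wrongly in both places where it appears, and that no correct figure is given elsewhere to put the reader right.

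**Conclusion.** The point holds as a mislabelled operating characteristic. Section 6.4 and the Synopsis print a beta of 0.8; the 12 per group belongs to a power of 0.80, which is a beta of 0.20. Taken literally, the printed beta would give 3 per group. Correcting it changes neither the sample size nor enrolment nor analysis, so it is a minor point. It gives no ground for calling the trial underpowered at the effect it assumes.

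The conclusion rests on d = 1.25 from a 2-point difference and SD 1.6, equal allocation, two-sided alpha 0.05 and a two-sample t-test. It does not test whether 1.25 is a sound planning value.

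The Synopsis needs more than the label. Its 0.917 and 60 participants conflict with the 1.25 and 56 of section 6.4 and do not reproduce at 80% power, so changing the word there would leave an incorrect calculation standing.

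**What to change.** - **Section 6.4:** replace the beta statement with: power 0.80 (beta 0.20), two-sided alpha 0.05. If an achieved power is wanted, add that 12 evaluable UC participants per arm give about 83% under a simple two-sample t-test with SD 1.6.
- **Synopsis:** replace the effect-size and sample-size statement as a whole with the section 6.4 calculation: d = 1.25, power 0.80, two-sided alpha 0.05, 12 evaluable UC participants per arm, 28 UC participants recruited, 56 participants in total. I carry over 28 and 56 as section 6.4 prints them.
- **Section 6.2** prints 30 UC participants and 30 healthy controls. It should be brought into line in the same edit, or the 60 will survive there.

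The cost is a few lines of wording. Correcting the label requires no change to enrolment, randomisation or analysis.

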6.5 STATISTICAL ANALYSIS

Intention-to-treat analysis regardless of dropout or study adherence is the primary analytic strategy. Primary and secondary continuous outcomes will be analyzed via linear repeated measures mixed models for testing of Group X Time interaction, with covariate adjustment over baseline and 4 weeks to characterize the intervention effects. In addition, outcomes at 5-8 weeks will identify and characterize any residual effects of the intervention during the washout phase and will be analyzed with respect to the intervention changes to determine the time course, if any, of residual effects. Covariates selected *a priori* based on the literature include age, sex, macronutrient intake, energy intake, and habitual physical activity level; other potential confounders identified at baseline may be added as required. A mediation analysis will be conducted via the PROCESS macro for SPSS version 2.13.2 to determine the indirect effect of dietary change on objective and subjective outcomes mediated by hypothesized beneficial alterations in the gut microbiota, while accounting for any potentially direct effects of EVOO.

[figure not shown]

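### The sample size in 6.4 fits a comparison of scores at one time point, but 6.5 tests a difference in change; whether 12 per arm gives 80% power depends on a pre-post correlation that the protocol does not state

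*Protocol*

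**What the plan says.** Section 6.4 takes its variance from an uncontrolled adult diet study, one of two whose effect sizes were "published means and standard deviations of a single group, pre-post study". The Table 1 row reads "Partial Mayo Score 5.8 (1.2) 1.2 (2.0) - 4.6 1.6 2.638281 16": baseline 5.8 (SD 1.2), post-diet 1.2 (SD 2.0), pooled SD 1.6.

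The target is then reduced: "We calculated effect size based on a 2 point (22%) reduction in the Partial Mayo Score", "with alpha 0.05 and beta 0.8" (read here as 80% power). The result is "Effect size was calculated to be 1.25, with a sample size of 12 participants per group", that is 24 participants with UC, raised to 28 for 16% dropout.

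Section 6.2 sets the comparison: "Participants within these two groups will be randomised after screening in a 1:1 ratio to nutrition intervention or usual care".

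Section 6.5 analyses primary continuous outcomes by "linear repeated measures mixed models for testing of Group X Time interaction", with the intervention effect taken over baseline and 4 weeks. The covariates chosen in advance are age, sex, macronutrient intake, energy intake and physical activity. The baseline Partial Mayo Score is not among them. No pre-post correlation, SD of change or within-person variance appears anywhere.

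**The concern.** A sample size calculation should use the variance of the quantity that is tested. Dividing 2 points by an SD of scores suits a comparison of the arms at one visit. A Group x Time test on two visits compares mean changes between arms, and its error is the SD of change. That SD can be larger or smaller than the SD of a score, depending on how strongly baseline and 4-week scores correlate.

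The power claim in 6.4 therefore does not belong to the analysis in 6.5. If the trial finds no difference in disease activity, readers will judge that result against an 80% figure that the planned test may or may not have.

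**Working it through.** **Inputs.** Difference 2 points, alpha 0.05, power 80%, SDs 1.2, 2.0 and pooled 1.6 (all section 6.4); 1:1 allocation (6.2); test over baseline and 4 weeks (6.5). Two-sidedness is not stated but is what reproduces the plan's n. The correlation r is an assumption and is shown as a range. Power is from the noncentral t distribution.

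**The plan's own figure.** 2/1.6 = 1.25. The text does not name 1.6 as the divisor, but the match is exact. A two-sided two-sample t-test with d = 1.25 gives 79.6% at 11 per arm and 83.3% at 12, so n = 12 reproduces. A one-sided test would need 9. The unrounded pooled SD is sqrt((1.2² + 2.0²)/2) = sqrt(2.72) = 1.65, so d = 1.21 and power at 12 is 81%. The rounding is immaterial.

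**The test in 6.5.** With two visits and balanced data, Group x Time equals a two-sample t-test on change, where

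Var(change) = SD0² + SD1² − 2·r·SD0·SD1.

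Four choices of SD:

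- A, table SDs in both arms: 1.44 + 4.00 − 4.8r = 5.44 − 4.8r
- B, equal SDs of 1.65: 2 × 2.72 × (1 − r) = 5.44(1 − r)
- C, equal SDs of 1.6 as printed: 5.12(1 − r)
- D, table SDs in the intervention arm and 1.2 throughout in usual care: mean of 5.44 − 4.8r and 2.88(1 − r), which is 4.16 − 3.84r

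Power for a 2-point difference in change, 12 per arm:

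| r | A | B | C | D |
|---|---|---|---|---|
| 0 | 52% | 52% | 54% | 63% |
| 0.3 | 65% | 67% | 70% | 77% |
| 0.5 | 77% | 81% | 83% | 88% |
| 0.7 | 90% | 96% | 96% | 97% |

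**Thresholds.** At 12 per arm, 80% power needs an SD of change of at most 1.671 (variance 2.793):

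- A: r = (5.44 − 2.793)/4.8 = 0.55
- B: r = 1 − 2.793/5.44 = 0.49
- C: r = 1 − 2.793/5.12 = 0.45
- D: r = (4.16 − 2.793)/3.84 = 0.36

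If all 28 recruited contribute (14 per arm), the limit is 1.818 (variance 3.305), and the thresholds are 0.44 (A), 0.39 (B), 0.35 (C) and 0.22 (D).

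**Baseline-adjusted 4-week contrast.** The residual SD is SD1·sqrt(1 − r²), which never exceeds the SD of the 4-week score. Estimating the baseline slope costs one degree of freedom and inflates the variance by about 1 + 1/20 = 1.05 at 12 per arm. With 21 degrees of freedom at r = 0:

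- SD 1.6: noncentrality 1.25 × sqrt(6/1.05) = 2.99, power 81%
- SD 1.65: noncentrality 1.213 × sqrt(6/1.05) = 2.90, power 79%

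At r = 0.5 the figures are 91% and 89%. These rest on a pooled 4-week SD of 1.6 to 1.65, which is what 2.0 in one arm and 1.2 in the other gives. If the 4-week SD were 2.0 in both arms, power would be about 63% at r = 0, 75% at 0.5 and 81% at 0.6.

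**The case against.** The arithmetic in 6.4 is sound. A reader might infer from the mismatch that the trial is underpowered or the calculation wrong; the documents support neither. They give no r, and above the thresholds the planned test reaches 80% or more, at high r more than the 83.3% behind the stated n. Case A is also the least favourable: it gives usual care the post-diet SD of 2.0, taken from a treated cohort whose mean fell by 4.6 points. Case D is at least as plausible and needs only r of about 0.36.

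Twelve per arm is the planned number after dropout. Section 6.5 makes intention-to-treat primary and a mixed model can use partial data, so the effective number may lie nearer 14. This stands, and is why both sets of thresholds are given.

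Two readings of the model could weaken the point. Section 7.1 puts the Partial Mayo Score into the weekly health checks; if those scores entered the model, the contrast would no longer be a simple two-visit change. However, the outcome table in 9.1 lists the primary outcome only at baseline, 4 and 8 weeks. The covariate wording in 6.5 could also be stretched to cover the baseline score, and other confounders may be added; but that score is not on the named list. Both readings are possible, and neither is what the text fixes.

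The reduction of the target from 4.6 to 2 points is conservative about the effect. It does not address which variance applies.

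**Conclusion.** The point holds as a mismatch between design and analysis. Section 6.4 uses the SD of a score; section 6.5, read as a two-visit test, needs the SD of change, and the link between them is not stated. For the protocol's own 2-point effect at 12 per arm, power runs from 52–63% at r = 0 through 65–77% at 0.3 and 77–88% at 0.5 to 90–97% at 0.7. It may fall below 80% if r is under about 0.36 to 0.55 (0.22 to 0.44 at 14 per arm), and is at least 80% above that.

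This rests on three assumptions: 1.6 was the divisor, only baseline and 4 weeks enter the test, and the published SDs carry over to this trial. It would also overstate matters to say that baseline adjustment secures 80% at any correlation: at r = 0 with SD 1.65 it gives about 79%, and less if the 4-week SD is larger. It does bring the analysis into line with the calculation already written.

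**What to change.** Preferred: in 6.5, define the primary disease-activity contrast as the between-arm difference in 4-week Partial Mayo Score, adjusted for the baseline score. In 6.4, say that 1.6 is taken as the SD of the 4-week score and that power at 12 per arm is about 79 to 81% at r = 0 and higher as r rises.

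Alternative: keep Group x Time on change, state the assumed r or SD of change with its source, and give power as a range over r at 12 and 14 per arm.

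Either way, say which visits enter the primary model and whether the weekly scores are used.

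The cost is a few sentences in 6.4 and 6.5. The baseline score is already collected, and no increase in sample size is needed. Under the alternative, the stated power may look less favourable.
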